APPENDIX 6 ECOG PERFORMANCE STATUS

Table 1: ECOG Performance Status

ECOG PERFORMANCE STATUS

0—Fully active, able to carry on all pre-disease performance without restriction

1—Restricted in physically strenuous activity but ambulatory and able to carry out work of a light or sedentary nature, e.g., light house work, office work

2—Ambulatory and capable of all selfcare but unable to carry out any work activities; up and about more than 50% of waking hours

3—Capable of only limited selfcare; confined to bed or chair more than 50% of waking hours

4—Completely disabled; cannot carry on any selfcare; totally confined to bed or chair

5—Dead

References: Oken MM, Creech RH, Tormey DC, et al. Toxicity and Response Criteria of the Eastern Cooperative Oncology Group. *Am J Clin Oncol* 1982;5:649-655.

APPENDIX 7 **RESPONSE EVALUATION CRITERIA IN SOLID TUMORS GUIDELINES (VERSION 1.1) WITH BMS MODIFICATIONS**

1 **EVALUATION OF LESIONS**

Solid tumors will be evaluated using Response Evaluation Criteria In Solid Tumors version 1.1 (RECIST 1.1) guideline with BMS modifications.¹

At baseline, tumor lesions/lymph nodes will be categorized as measurable or non-measurable as follows:

1.1 **Measurable**

Tumor lesions: Must be accurately measured in at least one dimension (longest diameter in the plane of measurement is to be recorded) with a minimum size of:

10 mm by CT/MRI scan (scan slice thickness no greater than 5 mm), or ≥ 2 x slice thickness if greater than 5mm.

Malignant lymph nodes: To be considered pathologically enlarged and measurable, a lymph node must be ≥ 15 mm in short axis when assessed by CT/MRI scan (scan slice thickness recommended to be no greater than 5 mm).

Lymph nodes merit special mention since they are normal anatomical structures which may be visible by imaging even if not involved by tumor. Pathological nodes which are defined as measurable and may be identified as target lesions must meet the criterion of a short axis of ≥ 15 mm by CT/MRI scan. Only the short axis of these nodes will contribute to the baseline sum. The short axis of the node is the diameter normally used by radiologists to judge if a node is involved by solid tumor. Nodal size is normally reported as two dimensions in the plane in which the image is obtained (for CT scan this is almost always the axial plane; for MRI the plane of acquisition may be axial, sagittal or coronal). The smaller of these measures is the short axis. For example, an abdominal node which is reported as being 20 mm x 30 mm has a short axis of 20 mm and qualifies as a malignant, measurable node. In this example, 20 mm should be recorded as the node measurement. All other pathological nodes (those with short axis ≥ 10 mm but < 15 mm) should be considered non-target lesions. Nodes that have a short axis < 10 mm are considered non-pathological and should not be recorded or followed.

Note: Lesions on X-Ray are not to be selected as Target or Non-Target Lesions.

1.2 **Non-Measurable**

All other lesions are considered non-measurable, including small lesions (longest diameter < 10 mm or pathological lymph nodes with ≥ 10 to < 15 mm short axis) as well as truly non-measurable lesions. Lesions considered truly non-measurable include: leptomeningeal disease, inflammatory breast disease, lymphangitic involvement of skin or lung, abdominal masses/abdominal organomegaly identified by physical exam that is not measurable by reproducible imaging techniques.

Note: Lesions on X-Ray are not to be selected as Target or Non-Target Lesions.

1.3 Special considerations regarding lesion measurability

1.3.1 Bone lesions

- Bone scan, PET scan and plain films are *not* considered adequate imaging techniques to measure bone lesions. However, these techniques can be used to confirm the presence or disappearance of bone lesions.
- Lytic bone lesions or mixed lytic-blastic lesions, with *identifiable soft tissue components*, that can be evaluated by cross sectional imaging techniques such as CT or MRI can be considered as measurable lesions if the *soft tissue component* meets the definition of measurability described above.
- Blastic bone lesions are non-measurable.

1.4 Baseline Documentation Of ‘Target’ And ‘Non-Target’ Lesions

When more than one measurable lesion is present at baseline all lesions up to a maximum of five lesions total (and a maximum of two lesions per organ) representative of all involved organs should be identified as target lesions and will be recorded and measured at baseline (this means in instances where patients have only one or two organ sites involved a maximum of two and four lesions respectively will be recorded).

Note: A maximum of two lesions can be selected per organ system. For example, a maximum of two lung lesions can be selected (selected from one lung or one lesion from each). A maximum of two lymph nodes can be selected at baseline, as the lymphatic system is considered one organ.

Target lesions should be selected on the basis of their size (lesions with the longest diameter), be representative of all involved organs, but in addition should be those that lend themselves to reproducible repeated measurements. It may be the case that, on occasion, the largest lesion does not lend itself to reproducible measurement in which circumstance the next largest lesion which can be measured reproducibly should be selected.

A sum of the diameters (longest for non-nodal lesions, short axis for nodal lesions) for all target lesions will be calculated and reported as the baseline sum diameters. If lymph nodes are to be included in the sum, then as noted above, only the short axis is added into the sum. The baseline sum diameters will be used as reference to further characterize any objective tumor regression in the measurable dimension of the disease.

All other lesions (or sites of disease) including pathological lymph nodes should be identified as non-target lesions and should also be recorded at baseline. Measurements are not required and these lesions should be followed as ‘present’, ‘absent’, or in rare cases ‘unequivocal progression’ (more details to follow). In addition, it is possible to record multiple non-target lesions involving the same organ as a single item on the case record form (eg, ‘multiple enlarged pelvic lymph nodes’ or ‘multiple liver metastases’).

2 RESPONSE CRITERIA

2.1 Evaluation of Target Lesions

- **Complete Response (CR):** Disappearance of all target lesions. Any pathological lymph nodes (whether target or non-target) must have reduction in short axis to < 10 mm.
- **Partial Response (PR):** At least a 30% decrease in the sum of diameters of target lesions, taking as reference the baseline sum diameters.
- **Progressive Disease (PD):** At least a 20% increase in the sum of diameters of target lesions, taking as reference the smallest sum on study (this includes the baseline sum if that is the smallest on study). In addition to the relative increase of 20%, the sum must also demonstrate an absolute increase of at least 5 mm. (Note: the appearance of one or more new lesions is also considered progression).
- **Stable Disease (SD):** Neither sufficient shrinkage to qualify for PR nor sufficient increase to qualify for PD, taking as reference the smallest sum diameters while on study.
- **Not Evaluable (NE):** If one or more target lesions cannot be measured or adequately assessed as either fully resolved or too small to measure (due to missing or poor quality images), and the sum of diameters of the remaining measured target lesions (if any) has not increased sufficiently to meet Progressive Disease as defined above.

2.1.1 *Special Notes on the Assessment of Target Lesions*

2.1.1.1 *Lymph nodes*

Lymph nodes identified as target lesions should always have the actual short axis measurement recorded (measured in the same anatomical plane as the baseline examination), even if the nodes regress to below 10 mm on study. This means that when lymph nodes are included as target lesions, the ‘sum’ of lesions may not be zero even if complete response criteria are met, since a normal lymph node is defined as having a short axis of < 10 mm. Case report forms or other data collection methods may therefore be designed to have target nodal lesions recorded in a separate section where, in order to qualify for CR, each node must achieve a short axis < 10 mm. For PR, SD and PD, the actual short axis measurement of the nodes is to be included in the sum of target lesions.

2.1.1.2 *Target lesions that become ‘too small to measure’*

While on study, all lesions (nodal and non-nodal) recorded at baseline should have their actual measurements recorded at each subsequent evaluation, even when very small (eg, 2 mm). However, sometimes lesions or lymph nodes which are recorded as target lesions at baseline become so faint on CT scan that the radiologist may not feel comfortable assigning an exact measure and may report them as being ‘too small to measure’. When this occurs it is important that a value be recorded on the case report form. If it is the opinion of the radiologist that the lesion has likely disappeared, the measurement should be recorded as 0 mm. If the lesion is believed to be present and is faintly seen but too small to measure, a default value of 5 mm should be assigned as the reference diameter. (Note: It is less likely that this rule will be used for lymph nodes since they usually have a definable size when normal and are frequently surrounded by fat such as in the retroperitoneum; however, if a lymph node is believed to be present and is faintly seen but too

small to measure, a default value of 5 mm should be assigned in this circumstance as well). This default value is derived from the 5 mm CT slice thickness (but should not be changed with varying CT slice thickness). The measurement of these lesions is potentially non-reproducible, therefore providing this default value will prevent false responses or progressions based upon measurement error. To reiterate, however, if the radiologist is able to provide an actual measure, that should be recorded, even if it is below 5 mm.

2.1.1.3 Lesions that split or coalesce on treatment

When non-nodal lesions ‘fragment’, the longest diameters of the fragmented portions should be added together to calculate the target lesion sum. Similarly, as lesions coalesce, a plane between them may be maintained that would aid in obtaining maximal diameter measurements of each individual lesion. If the lesions have truly coalesced such that they are no longer separable, the vector of the longest diameter in this instance should be the maximal longest diameter for the ‘coalesced lesion’.

2.2 Evaluation of Non-Target Lesions

This section provides the definitions of the criteria used to determine the tumor response for the group of non-target lesions. While some non-target lesions may actually be measurable, they need not be measured and instead should be assessed only qualitatively at the time points specified in the protocol.

- **Complete Response (CR):** Disappearance of all non-target lesions. All lymph nodes must be non-pathological in size (< 10mm short axis).
- **Non-CR/Non-PD:** Persistence of one or more non-target lesion(s)
- **Progressive Disease (PD):** Unequivocal progression of existing non-target lesions.

2.2.1 Special Notes on Assessment of Progression of Non-Target Disease

The concept of progression of non-target disease requires additional explanation as follows:

2.2.1.1 When the patient also has measurable disease

In this setting, to achieve ‘unequivocal progression’ on the basis of the non-target disease, there must be an overall level of substantial worsening in non-target disease such that, even in presence of SD or PR in target disease, the overall tumor burden has increased sufficiently to merit discontinuation of therapy. A modest ‘increase’ in the size of one or more non-target lesions is usually not sufficient to qualify for unequivocal progression status. Pleural effusions, pericardial effusions and ascites will not be followed as target or non-target lesions and will not contribute to response or progression. The designation of overall progression solely on the basis of change in non-target disease in the face of SD or PR of target disease will therefore be extremely rare.

2.2.1.2 When the patient has only non-measurable disease

This circumstance arises in some trials when it is not a criterion of study entry to have measurable disease. The same general concepts apply here as noted above, however, in this instance there is no measurable disease assessment to factor into the interpretation of an increase in non-measurable

disease burden. Because worsening in non-target disease cannot be easily quantified (by definition: if all lesions are truly non-measurable) a useful test that can be applied when assessing patients for unequivocal progression is to consider if the increase in overall disease burden based on the change in non-measurable disease is comparable in magnitude to the increase that would be required to declare PD for measurable disease: ie, an increase in tumor burden representing an additional 73% increase in ‘volume’ (which is equivalent to a 20% increase diameter in a measurable lesion). Examples include, an increase in lymphangitic disease from localized to widespread, or may be described as ‘sufficient to require a change in therapy’. If ‘unequivocal progression’ is seen, the patient should be considered to have had overall PD at that point. While it would be ideal to have objective criteria to apply to non-measurable disease, the very nature of that disease makes it impossible to do so; therefore the increase must be substantial.

2.2.2 New Lesions

The appearance of new malignant lesions denotes disease progression; therefore, some comments on detection of new lesions are important. There are no specific criteria for the identification of new radiographic lesions; however, the finding of a new lesion should be unequivocal: ie, not attributable to differences in scanning technique, change in imaging modality or findings thought to represent something other than tumor (for example, some ‘new’ bone lesions may be simply healing or flare of pre-existing lesions). This is particularly important when the patient’s baseline lesions show partial or complete response. For example, necrosis of a liver lesion may be reported on a CT scan report as a ‘new’ cystic lesion, which it is not.

NOTE: Fluid collections (pleural effusions, pericardial effusions, and ascites) will not be considered new lesions and will not contribute to response or progression. In the event a new fluid collection is seen on a post-baseline imaging exam, a comment may be made, but the appearance of a new fluid collection alone should not result in an assessment of Progressive Disease (PD). A lesion identified on a follow-up study in an anatomical location that was not scanned at baseline is considered a new lesion and will indicate disease progression. An example of this is the patient who has visceral disease at baseline and while on study has a CT or MRI brain ordered which reveals metastases. The patient’s brain metastases are considered to be evidence of PD even if he/she did not have brain imaging at baseline. A lesion identified on Chest X-Ray that was not present in prior CT can be considered a new lesion and will result in Progressive Disease (PD).

If a new lesion is equivocal, for example because of its small size, continued follow-up evaluation will clarify if it represents truly new disease. If repeat scans confirm there is definitely a new lesion, then progression should be declared using the date of the initial scan. While FDG-PET response assessments need additional study, it is sometimes reasonable to incorporate the use of FDG-PET scanning to complement CT scanning in assessment of progression (particularly possible ‘new’ disease). New lesions on the basis of FDG-PET imaging can be identified according to the following algorithm:

- 1) Negative FDG-PET at baseline, with a positive FDG-PET at follow-up is a sign of PD based on a new lesion.

- 2) No FDG-PET at baseline and a positive FDG-PET at follow-up: If the positive FDG-PET at follow-up corresponds to a new site of disease confirmed by CT, this is PD. If the positive FDG-PET at follow-up is not confirmed as a new site of disease on CT, additional follow-up CT scans are needed to determine if there is truly progression occurring at that site (if so, the date of PD will be the date of the initial abnormal FDG-PET scan). If the positive FDG-PET at follow-up corresponds to a pre-existing site of disease on CT that is not progressing on the basis of the anatomic images, this is not PD.

2.3 Response Assessment

2.3.1 Evaluation of Best Overall Response

The best overall response is the best response recorded from the start of the study treatment until disease progression or the last response recorded, taking into account any requirement for confirmation and censoring rules regarding subsequent therapy. The patient's best overall response assignment will depend on the findings of both target and non-target disease and will also take into consideration the appearance of new lesions. Furthermore, depending on the nature of the study and the protocol requirements, it may also require confirmatory measurement.

2.3.2 Time Point Response

At each protocol specified time point, a response assessment occurs. Table 2.3.2-1 provides a summary of the overall response status calculation at each time point for patients who have measurable disease at baseline. When patients have non-measurable (therefore non-target) disease only, Table 2.3.2-2 is to be used.

Target Lesions	Non-Target Lesions	New Lesions	Overall Response
CR	CR	No	CR
CR	Non-CR/non-PD	No	PR
CR	Not evaluated	No	PR
PR	Non-PD or not all evaluated	No	PR
SD	Non-PD or not all evaluated	No	SD
Not all evaluated	Non-PD	No	NE
PD	Any	Yes or No	PD
Any	PD	Yes or No	PD
Any	Any	Yes	PD

CR = complete response, PR = partial response, SD = stable disease, PD = progressive disease and NE = inevaluable

Table 2.3.2-2: Time Point Response: Patients With Non-Target Disease Only		
Non-Target Lesions	New Lesions	Overall Response
CR	No	CR
Non-CR/non-PD	No	Non-CR/non-PD ^a
Not all evaluated	No	NE
Unequivocal PD	Yes or No	PD
Any	Yes	PD
CR = complete response, PD = progressive disease and NE = inevaluable		

^a Non-CR/non-PD is preferred over SD for non-target disease since SD is increasingly used as endpoint for assessment of efficacy in some trials so to assign this category when no lesions can be measured is not advised.

2.3.3 Best Overall Response

Best response determination of complete or partial response requires confirmation: Complete or partial responses may be claimed only if the criteria for each are met at a subsequent time point of ≥ 4 weeks (28 days) later. In this circumstance, the best overall response can be interpreted as in Table 2.3.3-1. When SD is believed to be best response, it must meet the protocol specified minimum time from the date of first treatment or randomization date.

For example, if the first scheduled follow-up imaging visit is Week 6 (± 7 days) for a particular protocol, a Best Response of SD can only be made after the subject is on-study for a minimum of 6 weeks (42 days) minus 7 days, for an absolute minimum time on-study of 35 days from the reference start date (reference date is considered Day 1 on study). If the subject is not on-study for at least this amount of time, any tumor assessment indicating stable disease before this time period will have a Best Response of NE unless PD is identified.

Special note on response assessment: When nodal disease is included in the sum of target lesions and the nodes decrease to ‘normal’ size (< 10 mm), they may still have a measurement reported on scans. This measurement should be recorded even though the nodes are normal in order not to overstate progression should it be based on increase in size of the nodes. As noted earlier, this means that patients with CR may not have a total sum of ‘zero’ on the case report form (CRF).

Table 2.3.3-1: Best Overall Response (Confirmation of CR and PR Required)		
Overall Response First Time Point	Overall Response Subsequent Time Point	Best Overall Response
CR	CR	CR
CR	PR	SD, PD OR PR ^a
CR	SD	SD provided minimum criteria for SD duration met, otherwise, PD
CR	PD	SD provided minimum criteria for SD duration met, otherwise, PD

Table 2.3.3-1: Best Overall Response (Confirmation of CR and PR Required)		
Overall Response First Time Point	Overall Response Subsequent Time Point	Best Overall Response
CR	NE	SD provided minimum criteria for SD duration met, otherwise, NE
PR	CR	PR
PR	PR	PR
PR	SD	SD
PR	PD	SD provided minimum criteria for SD duration met, otherwise, PD
PR	NE	SD provided minimum criteria for SD duration met, otherwise, NE
NE	NE	NE

CR = complete response, PR = partial response, SD = stable disease, PD = progressive disease, and NE = inevaluable

^a If a CR is truly met at first time point, then any disease seen at a subsequent time point, even disease meeting PR criteria relative to baseline, makes the disease PD at that point (since disease must have reappeared after CR). Best response would depend on whether minimum duration for SD was met. However, sometimes ‘CR’ may be claimed when subsequent scans suggest small lesions were likely still present and in fact the patient had PR, not CR at the first time point. Under these circumstances, the original CR should be changed to PR and the best response is PR.

2.3.4 Confirmation Scans

Verification of Response: To be assigned a status of CR or PR, changes in tumor measurements must be confirmed by consecutive or subsequent repeat assessments that should be performed no less than 28 days after the criteria for response are first met. Subsequent documentation of a CR may provide confirmation of a previously identified CR even with an intervening NE or PR (eg, CR NE CR or CR PR CR). Subsequent documentation of a PR may provide confirmation of a previously identified PR even with an intervening NE or SD (eg, PR NE PR or PR SD PR). However, only one (1) intervening time point will be allowed between PR/CRs for confirmation.

Verification of Progression: Progression of disease should be verified in cases where progression is equivocal. If repeat scans confirm PD, then progression should be declared using the date of the initial scan. If repeat scans do not confirm PD, then the subject is considered to not have progressive disease.

REFERENCES

¹ Eisenhauer EA, Therasse P, Bogaerts J, et al. New response evaluation criteria in solid tumors: revised RECIST guideline (version 1.1). Eur J Cancer 2009; 45: 228-47.

**APPENDIX 8 RADIOGRAPHIC ASSESSMENT FOR NEURO-ONCOLOGY
(RANO) CRITERIA FOR HIGH-GRADE GLIOMAS**

Table 1: Summary of Proposed Radiographic Assessment for Neuro-Oncology

Criterion	Complete Response	Partial Response	Stable Disease	Progressive Disease
T1 gadolinium enhancing disease	None	≥ 50% ↓	< 50% ↓ but < 25% ↑	≥ 25% ↑*
T2/FLAIR	Stable or ↓	Stable or ↓	Stable or ↓	↑*
New lesion	None	None	None	Present*
Corticosteroids	None	Stable or ↓	Stable or ↓	NA†
Clinical status	Stable or ↑	Stable or ↑	Stable or ↑	↓*
Requirement for response	All	All	All	Any*

Abbreviations: RANO, Response Assessment in Neuro-Oncology; CR, complete response; PR, partial response; SD, stable disease; PD, progressive disease; FLAIR, fluid-attenuated inversion recovery; NA, not applicable.

* Progression occurs when this criterion is present.

† Increase in corticosteroids alone will not be taken into account in determining progression in the absence of persistent clinical deterioration.

NOTE. All measurable and nonmeasurable lesions must be assessed using the same techniques as at baseline.

Reference: Wen PY, Macdonald DR, Reardon DA, et al. Updated Response Assessment Criteria for High-Grade Gliomas: Response Assessment in Neuro-Oncology Working Group J Clin Oncol 2010;28-1:3059-3067.

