10.3.1 Efficacy Analyses

Endpoint Definition	Statistical Analysis Methods
Primary	

ORR (based on BICR assessments) is defined as the number of participants with a best overall response of confirmed CR or PR divided by the number of all randomized participants. Best overall response is defined as the best response designation, as determined by BICR, recorded between the date of randomization and the date of objectively documented progression (per RECIST v1.1 or RANO criteria) or the date of subsequent therapy, whichever occurs first. For participants without documented progression or subsequent therapy, all available response designations will contribute to the BOR determination. For participants who continue treatment beyond progression, the BOR will be determined based on response assessments up to the time of initial RECIST 1.1 progression.
	
BICR-assessed objective response rate (ORR) using disease specific response criteria: Response Evaluation Criteria in Solid Tumors (RECIST 1.1), and Response Assessment for Neuro-Oncology (RANO) criteria for primary CNS neoplasms.
 
BICR-assessed ORR will be summarized by binomial response rates and their corresponding two-sided 95% exact CIs using Clopper-Pearson method.

Secondary	

DOR (based on BICR assessments) is defined as the time from first confirmed response (CR or PR) to the date of the first documented tumor progression as determined using RECIST 1.1 or RANO criteria or death due to any cause, whichever occurs first.
 
Participants who start subsequent therapy without a prior reported progression will be censored at the last evaluable tumor assessments prior to initiation of the subsequent anticancer therapy. Participants who die without a reported prior progression will be considered to have progressed on the date of their death.
 
Participants who neither progress nor die will be censored on the date of their last evaluable tumor assessment.
	
BICR-assessed duration of response (DOR) will be estimated for all randomized participants who achieve confirmed PR or CR using the Kaplan-Meier (KM) product-limit method. Median values of DOR, along with two-sided 95% CI using Brookmeyer and Crowley method, will also be calculated. Probability of achieving $DOR \geq 6$ months will be calculated using KM method with 95% CI.

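### Appendix 7 gives two incompatible best responses for CR, then PR with visible disease, then CR, so such a record can count as a responder or a non-responder in the primary ORR

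*Combined protocol and SAP*

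**What the plan says.** Three parts of the protocol bear on this point.

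- **Confirmation rule (Appendix 7, Section 2.3.4).** "Subsequent documentation of a CR may provide confirmation of a previously identified CR even with an intervening NE or PR". The text gives examples ("eg, CR NE CR or CR PR CR") and a limit: "only one (1) intervening time point will be allowed between PR/CRs for confirmation".
- **Rule for disease after CR (Appendix 7, Table 2.3.3-1, footnote a).** If the first CR was truly met, "any disease seen at a subsequent time point, even disease meeting PR criteria relative to baseline, makes the disease PD at that point". The footnote continues: "Best response would depend on whether minimum duration for SD was met". It has a second branch. If later scans suggest that small lesions were probably there all along, "the original CR should be changed to PR and the best response is PR".
- **Primary endpoint (Section 10.3.1).** ORR is "the number of participants with a best overall response of confirmed CR or PR divided by the number of all randomized participants", as read by BICR. Best overall response is the best designation "recorded between the date of randomization and the date of objectively documented progression", or up to subsequent therapy if that comes first.

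Section 9.1.3 sets the minimum for a best response of SD at 77 days from first dose. The schedules in Section 2 put scans every 12 weeks, ± 7 days.

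**The concern.** The confirmation rule treats a middle PR as a gap that can be bridged. Footnote a treats disease on that same scan as progression. To confirm the first CR as a CR, Section 2.3.4 must accept that it was a true CR, and that is the condition under which footnote a declares PD. Where disease is seen on the middle scan, both rules cannot be applied to the record.

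The choice reaches the primary endpoint because progression closes the window for best overall response, so the later CR no longer counts. It also decides whether the participant contributes a DOR at all and when a PFS event is recorded. A primary endpoint should follow from the scans alone. Two unranked rules leave room to choose after the result is visible.

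**Working it through.** **1. Apply each rule to one record.** Take CR at week 12, PR with visible disease at week 24 and CR at week 36 (days 84, 168 and 252).

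- Confirmation interval: 252 − 84 = 168 days, against a required 28.
- Intervening time points: one, which is the number allowed.
- SD minimum: the first scan falls at day 84, or day 84 − 7 = 77 at the earliest, so the 77-day minimum is met on schedule.

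| Rule | Middle scan | Best overall response | ORR | DOR and PFS |
|---|---|---|---|---|
| Section 2.3.4 | bridged | confirmed CR | responder | DOR starts week 12; no PFS event at week 24 |
| Footnote a, first CR true | PD | SD (PD if the minimum is not met) | non-responder | no DOR; PFS event at week 24 |
| Footnote a, first CR re-read as PR | PR | PR | responder | DOR starts week 12; no PFS event at week 24 |

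Responder status therefore splits between the first two rows. Between the first and third rows only the category (CR or PR) differs.

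**2. Find where the rules do not conflict.** Table 2.3.2-1 in Appendix 7 also assigns an overall PR when target lesions are in CR, non-target lesions were not evaluated and there is no new lesion. No disease is seen on such a scan, so footnote a is not triggered. Section 2.3.4 then applies alone and gives a confirmed CR. CNS tumors are read by RANO and lie outside this appendix.

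**3. Reproduce the plan's precision table (Section 10.1).** The exact 95% limits for x responders of n are the 2.5% quantile of Beta(x, n − x + 1) and the 97.5% quantile of Beta(x + 1, n − x). For 30/76 this gives 0.284 and 0.514, matching the stated (0.28, 0.51). All ten rows of the table reproduce to two decimals.

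**4. Size per participant.** One participant is 1/76 = 1.3 points. The number reclassified is an assumption, shown from 0 to 3:

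| Reclassified | ORR | Exact 95% CI |
|---|---|---|
| 0 (30/76) | 39.5% | 28.4–51.4 |
| 1 (29/76) | 38.2% | 27.2–50.0 |
| 2 (28/76) | 36.8% | 26.1–48.7 |
| 3 (27/76) | 35.5% | 24.9–47.3 |

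At the tTMB interim analysis, with about 50 combination-arm participants, one participant is 1/50 = 2 points.

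**5. How often might the sequence occur?** The documents do not say. One illustration is a lymph node near the 10 mm limit for CR. If p is the probability that it measures below 10 mm, the chance of CR, PR, CR is p²(1 − p). For an assumed true short axis of 8 to 9 mm and a measurement SD of 1 to 1.5 mm, p runs from 0.977 down to 0.748, and the chance runs from 2.2% to 14.1%. With an assumed CR rate of 5 to 15% (about 4 to 11 of 76), and supposing that every CR had such a node, the expected count is 4 × 0.022 = 0.1 to 11 × 0.141 = 1.6. That supposition is extreme, so 0 to 1 participant per population is a reasonable working figure for the sequence itself.

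**The case against.** A reader might infer that every CR, PR, CR record is classified two ways. The documents do not support that: where the PR reflects only unevaluated non-target lesions, the rules agree. It would also be wrong to argue from the CR-then-PR row of Table 2.3.3-1, which never lists CR as an outcome. That table covers two time points, and its CR-then-NE row does not list CR either, although Section 2.3.4 plainly accepts CR, NE, CR.

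A second objection is that the verification-of-progression paragraph in Section 2.3.4 already settles the matter, because a third scan showing CR fails to confirm PD. It may do so where progression is equivocal, and a node hovering at 10 mm is a natural example. But the paragraph is confined to equivocal cases, whereas footnote a declares PD without that qualifier. Likewise, the permissive wording of the confirmation rule leaves discretion without saying when to use it.

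The strongest objection concerns size. Noise around a persistent node below 10 mm mostly leads to CR, or to PR on re-reading, and both are responders. The 1.3-point shift belongs only to the true-CR branch, with disease that reappears and then clears, and the node calculation does not estimate how often that happens. This objection stands.

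Finally, the Imaging Manual and the later SAP may already set an order of precedence. They are not part of these documents, and the conflict would remain in the protocol text either way.

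**Conclusion.** The contradiction is real but narrow. It concerns RECIST-assessed tumors in which a CR is followed by a PR scan with visible disease and then by a CR. For that record the protocol supports confirmed CR, SD or PR, and does not say which.

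The effect is 1.3 points of ORR for each participant moved from responder to non-responder at n=76, together with a lost DOR contribution and an earlier PFS event. The working figure of 0 to 1 such sequences per population rests on assumed CR rates, node sizes and measurement error. The number that would change responder status is smaller and unknown. A reader might infer that the primary ORR is materially inflated; nothing in the documents shows that, and the trial's conclusion is unlikely to turn on this point. It should still be corrected, because it is a rule for the primary endpoint and costs almost nothing to settle before reads are finalized.

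**What to change.** Reword Appendix 7, Section 2.3.4 to say:

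- A later CR confirms an earlier CR across one intervening NE, or across one intervening PR that was assigned only because non-target lesions were not evaluated.
- Where disease is seen at the intervening scan, footnote a to Table 2.3.3-1 governs. The scan is PD if the first CR was true; otherwise the first CR is re-read as PR and confirmed as PR.
- Whether the verification-of-progression paragraph applies to this case.

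Simply removing PR from the confirmation sentence would go too far. It would deny confirmation to records in which no disease was seen and to which footnote a does not apply.

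Carry the same rule into the BICR charter (or the imaging vendor documents that serve as one) and the SAP before reads are finalized. The cost is a few lines of text. The ORR or the CR rate may come out very slightly less favourable.
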